Study design	A multicenter parallel, open label, superiority randomized controlled trial, with an alongside implementation study.
Aims	To determine the clinical effectiveness, tolerability, and safety of intravenous ferric carboxymaltose (intervention) versus oral ferrous sulphate (control) for treating iron deficiency anemia in postpartum women.
	To evaluate the implementation outcomes (acceptability and feasibility) of using intravenous ferric carboxymaltose in treating postpartum anemia in Nigeria.
Objective(s)	 To determine the clinical effectiveness of intravenous ferric carboxymaltose versus oral ferrous sulphate in postpartum women with moderate to severe iron deficiency anemia. To determine the incidence of adverse drug events including the incidence of hypophosphatemia in the mother and adherence with the use of intravenous ferric carboxymaltose and oral ferrous sulphate for treatment of postpartum anemia. We will measure Vitamin D, alkaline phosphatase, total procollagen type 1 N-terminal propeptide (P1NP), fibroblast growth factor 23 (FGF23), calcium (Ca), phosphate (PO₄), which are biomarkers of phosphorus homeostasis and bone turnover. To determine the acceptability of Intravenous Ferric carboxymaltose to women and health care professionals

	• To determine the feasibility and organizational readiness for implementing the use of intravenous ferric carboxymaltose in treating postpartum anemia in Nigeria.
Number of participants	1,400 women
Participant selection criteria	 Women aged 15 to 49 years. Between six and 48 hours after birth. Baseline (enrolment) moderate or severe anemia (Hb < 10g/dl). Able and willing to give written informed consent
Intervention product, dose, and route of administration	Ferric carboxymaltose, single dose of 20mg/kg (not exceeding 1000mg), Intravenous route
(Control) product, dose, and route of administration	Ferrous sulphate, 200mg (65mg elemental iron) two times daily. Oral route.
Duration of each woman's participation	6 months
Follow-up	2 weeks (±3 days), 6 (±1) weeks, 12 (±2) weeks and 6(±1) months postpartum.
Study duration	36-months

[figure not shown]

TABLE OF CONTENTS

ATTESTA	ATIONS	4
PROTOC	COL SYNOPSIS	5
TABLE O	OF CONTENTS	7
LIST OF 1	TABLES	11
LIST OF I	FIGURES	11
LIST OF A	ABBREVIATIONS	12
GLOSSAI	RY OF TERMS	13
INTRODI	UCTION	14
1.1	Background	14
2 STUDY	Y OBJECTIVES	17
2.1	Aims	17
2.2	Objectives	17
з оитсс	OMES	18
3.1	Clinical outcomes	18
3.2	Implementation outcomes	19
4 STUDY	Y DESIGN	20

Table 3: Assessment and schedule for study participants	32
Table 4: Adverse effects grading with unique clinical descriptions of severity	37
Table 5: Target stakeholders for qualitative data collection	47
Table 6: Framework for triangulating methods	49
Table 7: Timeline of data collection	50

LIST OF FIGURES

Figure 1: Map of Nigeria indicating the four selected states for the study with key population and service indices	20
Figure 2: Prospective (clinical trial) study design flowchart	. 25
Figure 3: Implementation evaluation guided by the Consolidated Framework for Implementation Research (CFIR)	۱4۰

LIST OF ABBREVIATIONS

AE Adverse event
AE(s) Adverse Event(s)

AIM Acceptability of intervention measure

AIP Anemia in pregnancy

AKTH Aminu Kano Teaching Hospital

ALP Alkaline phosphatase

CA Calcium

CFIR Consolidated framework of Implementation Research

CI Confidence interval

CMUL College of Medicine, University of Lagos

CRA Clinical research associate

CRF Case report form

DSMC Data and Safety Monitoring Committee

FGF23 Fibroblast growth factor 23 (FGF23)

FGD Focus group discussion

FIM Feasibility of intervention measure

GCP Good Clinical Practice

Hb Hemoglobin

IDA Iron deficiency anemia
IRB Institutional Review Board
KII Key informant interview

LBW Low birth weight

LMIC Low- and middle-income countries

LUTH Lagos University Teaching Hospital

P1NP Procollagen type 1 N-terminal propeptide (P1NP)

POCT Point of care test PO₄ Phosphate (PO₄)

PPD Postpartum depression

RCT Randomized controlled trial.
RNA Research Nurse Assistant

SAE Serious adverse event

SOP Standard Operating Procedure

GLOSSARY OF TERMS

Assessment	A procedure used to generate data required by the study					
Chief Investigator	The Chief Investigator (CI) is the overall lead researcher for the project and takes overall responsibility within the team of researchers for the design, conduct and reporting of the study.					
Control drug	The study drug (oral ferrous sulphate) used as a comparator to reduce assessment bias, assess internal study validity, and/or evaluate comparative effects of the investigational drug.					
Enrolment	Point/time of patient entry into the study; the point at which informed consent must be obtained (i.e., prior to starting any of the procedures described in the protocol)					
Investigational drug	The study drug (ferric carboxymaltose) whose properties is being tested in the study.					
Premature patient withdrawal	Point/time when the patient exits from the study prior to the planned completion of all study drug administration and assessments; at this time study drug administration is discontinued, and no further assessments a planned					
Principal Investigator	The Principal Investigator (PI) is the individual responsible for the conduct of the research at the state level and have coordinating and oversight responsibilities for all study site in their state.					
Site Coordinator (Clinician)	The site coordinator (clinician), SC is the person at each study site responsible for the day to day running of the research project.					
Source Document	A source document is a document in which data collected for a clinical trial is first recorded e.g patient's clinical note/file, registers, logs etc. This data is usually later entered in the case report form.					
Study drug	Any drug (control or investigational) administered to the patient as part of the required study procedures; includes investigational drug and any control drugs					
Study drug discontinuation	Point/time when patient permanently stops taking study drug for any reason; may or may not also be the point/time of premature patient withdrawal					

Study ID	A number assigned to each patient that is enrolled into the study. When combined with the center number, a unique identifier for each patient in the study is created. This is done automatically during the randomization process.
Variable	Information used in the data analysis; derived directly or indirectly from data collected using specified assessments at specified time points

INTRODUCTION

1.1 Background

Anemia in pregnancy is a major public health burden with a high incidence in low- and middle-income countries (LMICs) such as Nigeria (1). It is most commonly caused by iron deficiency, which accounts for 50–75% (2). Postnatal anemia may result from untreated antenatal anemia or as a result of blood loss that occurs during birth. (3), and its prevalence in LMICs has been estimated to range from 50 to 80% (4). A study in Eastern Nigeria found anemia at 48 hours and six weeks postpartum to be 73% and 48% respectively, in a cohort of 202 women followed from late pregnancy until six weeks postpartum (5).

Anemia and iron deficiency anemia in pregnancy lead to increased morbidity and mortality for the mother and affects the neonates adversely (6). Specifically, postnatal anemia increases the risk of infection, leads to poor wound healing, and causes fatigue and depression in the mother (7). It also adversely affects breastfeeding, due to insufficient milk production, can reduce bonding between women and their newborn as a result of weakness and fatigue (3, 4, 8).

Oral iron is used routinely for the treatment of mild to moderate anemia in the postnatal period, while blood transfusion is offered for severe anemia or symptomatic women with moderate anemia (3). Oral iron, though inexpensive, causes significant gastrointestinal adverse effects such as vomiting, constipation, diarrhea, and abdominal pain (9), limiting adherence to this vital intervention which may pose a challenge in achieving optimum correction of anemia by the end of the postnatal period. Adherence to oral iron is reportedly low, with only 16% of women fully compliant with their treatment in a study among pregnant women in Cameroon, one of Nigeria's neighboring countries (10).

Intravenous iron can be given as a single dose and is suitable for patients who respond poorly to oral iron and moderately anemic women that require more rapid iron replacement for symptom control (3). Intravenous iron corrects anemia faster and in fewer doses than oral iron, requiring less patient-provider interaction, a situation that is ideal in LMICs where loss to follow up is common for various reasons especially in the postpartum period. Froessler et al. reported on 214 women with iron deficiency anemia, 107 of whom were recruited postpartum, and found a more rapid increase in serum ferritin with administration of intravenous iron sucrose compared with oral ferrous sulphate in the treatment of postpartum anemia (11). A randomized controlled trial by Vanobberghen et al. conducted in Tanzania (230 women) found intravenous ferric carboxymaltose to be more effective than oral iron

for treating postpartum anemia and iron deficiency anemia with an almost five times greater odds of normalized hemoglobin level and a significantly higher ferritin level (12).

Although clinicians are aware of intravenous iron, its use is not widespread in most obstetric units in Nigeria. An equivalence randomized controlled trial studied 284 postpartum women in southeastern Nigeria and found total dose infusion of high molecular weight iron dextran to be as effective as oral iron (III) hydroxide polymaltose tablets in correcting anemia by six weeks postpartum, when administered to postpartum women 48 hours or later after delivery (13). In most health facilities in Nigeria, women are often discharged home after delivery on oral iron (5) without strict monitoring of compliance to the medication. The uptake of postnatal care in Nigerian women is approximately 40% (14, 15), with one survey showing 37% of women receiving postnatal care within 2 days of delivery, 3% between 3 days and 6 weeks postpartum, while 60% did not receive any postpartum care (15). Most of the women discharged on oral iron will therefore not have the chance to have their hemoglobin levels or clinical states re-examined to determine whether their anemia has resolved.

There are many safe parenteral iron preparations, such as iron sucrose, iron polymaltose, ferric carboxymaltose and iron isomaltoside, with few adverse effects (16). Ferric carboxymaltose is safe and effective but was recently found to reduce serum phosphate levels (17). However, the associated reduction in serum phosphate concentration is not thought to be clinically relevant in pregnancy, probably because it is given in just a few doses. In studies conducted in pregnant women, the serum phosphate has been found to return to normal within a short period of time (18-20). The main disadvantage with intravenous iron preparations is that they are relatively expensive (16) but as they offer the potential to avoid blood transfusion and its complications and reduce maternal morbidity and mortality this cost might be mitigated.

As postpartum anemia is highly prevalent in Nigeria and has a significant detrimental impact on the physical and mental health of women and their newborns, we propose a randomized controlled trial examining the clinical effectiveness of intravenous ferric carboxymaltose versus oral ferrous sulphate for moderate to severe anemia in postpartum Nigerian women. Recognizing the volatility of introducing such treatment in Nigeria, we also propose an alongside implementation study to better understand the implementation climate and assess key implementation outcomes.

2 STUDY OBJECTIVES

2.1 Aims

- a) To determine the clinical effectiveness, tolerability, and safety of intravenous ferric carboxymaltose (intervention) versus oral ferrous sulphate (control) for treating moderate to severe iron deficiency anemia in postpartum women (population).
- b) To evaluate implementation of intravenous ferric carboxymaltose in treating postpartum anemia in Nigeria.

2.2 Objectives

- a) To determine the clinical effectiveness of intravenous ferric carboxymaltose versus oral ferrous sulphate in postpartum women with moderate to severe iron deficiency anemia by conducting a randomized trial.
- b) To determine the incidence of adverse drug events including the incidence of hypophosphatemia in the mother and adherence with the use of intravenous ferric carboxymaltose and oral ferrous sulphate for treatment of postpartum anemia. We will evaluate biomarkers of calcium and phosphate homeostasis and bone turnover and measure vitamin D, alkaline phosphatase, procollagen type 1 N-terminal propeptide (P1NP), fibroblast growth factor 23 (FGF23), calcium and Phosphate levels.
- c) To evaluate the acceptability and feasibility of using intravenous ferric carboxymaltose in treating postpartum anemia in Nigeria by conducting an alongside implementation study.

3 OUTCOMES

3.1 Clinical outcomes

3.1.1 Primary outcome

Proportion of participants who are non-anemic at six weeks postpartum. Non-anemic state is defined as hemoglobin level ≥ 11.0 g/dl.

3.1.2 Secondary outcomes

- a) Proportion of women with postpartum depression, measured using the Edinburgh Postnatal Depression Scale at six weeks and six months postpartum.
- b) Change in mean postpartum hemoglobin levels at two weeks and six weeks postpartum.
- c) Achievement of a non-anemic state (Hb≥11.0g/dl) at six months postpartum.
- d) Prevalence of moderate/severe anemia at six weeks and six months postpartum. Moderate anemia is defined as hemoglobin level 7.0-9.9g/dl and severe anemia as hemoglobin level <7.0g/dl.
- e) Change in mean serum ferritin, serum transferrin, serum iron and % transferrin saturation at two weeks and six weeks postpartum.
- f) Need for blood transfusion after iron treatment during the first 6 weeks postpartum.
- g) Prevalence of fatigue at six weeks and six months postpartum, measured using the Fatigue Severity Scale (revised FSS-5R version) (22).
- h) Proportion of women with secondary postpartum hemorrhage after treatment. This will be defined as excessive bleeding requiring surgical intervention or blood transfusion from 24 hours after delivery till 12 weeks postpartum (23).
- i) Proportion of infants being breastfed (exclusive and any) at six weeks and six months postpartum.
- j) Prevalence of impaired maternal-infant bonding at six weeks and six months postpartum measured using the Mother-to-Infant Bonding Scale (MIBS) (20).
- k) Incidence confirmed or suspected maternal infection within 6 weeks of birth, as defined by a new prescription of antibiotics for presumed perineal wound-related infection, endometritis or uterine infection, urinary tract infection or other systemic infection (clinical sepsis).
- I) Incidence of hypophosphatemia at two weeks and six weeks postpartum. We will measure vitamin D, alkaline phosphatase, P1NP, FGF23, Ca, PO₄, which are biomarkers of phosphorus homeostasis and bone turnover. Hypophosphatemia is defined as serum phosphate level <2.5mg/dL (0.81mmol/L). Mild hypophosphatemia as 2-2.5 mg/dL (0.65-0.81 mmol/L), moderate as 1-2 mg/dL (0.32-0.65 mmol/L), and severe as <1 mg/dL (0.32 mmol/L).
- m) Incidence of early neonatal death, defined as death of newborn from enrolment of the mother to before seven completed days.
- n) Incidence of late neonatal death, defined as death of the newborn from enrolment of the mother to before 28 completed days.
- o) Incidence of infant death, defined as death from enrolment before the age of six months.

- p) Incidence of post-natal maternal death from enrolment up to six weeks and at six months postpartum.
- q) Incidence of adverse drug events.
- r) Quality of life measured using the WHOQOL BREF at enrollment, six weeks, and six months post-partum.

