4.9 Laboratory evaluations

Standard clinical laboratory evaluations will be performed as follows:

- Hemoglobin concentration with the Hemocue haemoglobinometer at screening, two and six weeks and six months postpartum. Complete the *Hb check worksheet* as appropriate (*Appendix i*).
- Malaria rapid diagnostic test (RDT) with SD BIOLINE Malaria Ag P.f at enrollment, two and six weeks
 postpartum and if symptomatic for malaria at any time. Complete the *Malaria POCT worksheet* as
 appropriate (Appendix ii).
- Full blood count at baseline (enrollment), two weeks, six weeks, and six months postpartum. At each visit, 4mls of blood will be collected in an EDTA vacutainer. *Complete blood sample collection log for study visits on REDCap (Appendix iii)*.
- Iron profile: comprises serum iron, serum ferritin, serum transferrin and percentage transferrin saturation will be done at baseline (enrollment), six weeks and six months postpartum. At each visit, 4mls of blood will be collected into a Serum separating tubes (SST) tube. *Complete blood sample collection log for study visits on REDCap*
- Maternal serum phosphate and other biomarkers: The biomarkers of phosphate homeostasis and bone turnover to be measured are Vitamin D, alkaline phosphatase, total procollagen type 1 N-terminal propeptide (P1NP), fibroblast growth factor 23 (FGF23), calcium (Ca) and phosphate (PO4) at baseline (enrollment), 2 weeks (Ca, PO4 and ALP only) and at 6 weeks postpartum. Two (2) SST tubes will be used for sample collection and 4mls of blood will be collected in each tube.
 Complete blood sample collection log for study visits on REDCap.

All samples aside the point of care tests (POCT) will be analyzed at Synlab (an internationally accredited medical laboratory). As a third-party, a contract is in place between the University of Lagos and Synlab. The following steps will be taken at blood sampling:

- Research nurse assistants will collect blood sample as indicated for study visit using an appropriate vacutainer system.
- Complete the *laboratory tests request form* (Appendix iv) with participant's study ID, study site code and visit type (PP-1 to PP-4) to accompany the samples to the lab.
- Document date and time samples were taken and type of test in blood sample collection log on REDCap for study visit.
- Call the dispatch rider for samples pick up within 2-3 hours of sample collection.

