4.10.2 Enrollment and randomization visit (Visit 1)

Enrollment (visit-1) will preferably take place during the same visit/time as the screening (visit-0) or very shortly after within 6-48 hours after delivery.

• Once the participant has been screened and determined to meet study eligibility criteria and complete the informed consent document,

The following additional steps will be taken:

1. Go to Sealed Envelope and randomize the participant into a study arm.

- The participant will be assigned a study ID which will be used to identify the participant throughout the study.
- Complete the enrollment log sheet (*Appendix vii*) with the participant's assigned study ID and treatment arm.
- The study ID only will also be written on her clinical case-notes (source document).

2. Go to REDCap

- Complete participant's biodata and locator form (Appendix viii): For each participant, the research nurse (RN) will obtain contact information, which will include the participant's phone number, her partner's phone number, her home address, major landmark to her home, occupation, and other necessary information as provided by the participant. The RN should determine the best way to collect this information for each study participant and complete it in the participant's biodata and locator form. If a participant misses a scheduled appointment (follow-up or end of study visit), the research staff will try to establish communication with the participant through authorized possible means (e.g., phone, emails or visiting the participant's home or workplace). The need to complete all scheduled follow up visits must be emphasized to all study participants at enrolment and at every visit.
- Take relevant medical history and concomitant medication information.
- Do a physical examination
- Evaluate for the presence of any symptom and sign (adverse event(s) AEs)) and if any,
 complete and submit the adverse event e-form (Appendix ix).
- **Complete enrollment e-CRF (***Appendix x***)** and relevant source document (SD) to document relevant baseline observation.
- Take blood samples for laboratory tests complete the blood sample collection log.
- Administer study drug (intervention or control) according to randomization and protocol for study drug administration (section 4.6.1)

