4.10.3 Follow-up visits (2, 6, and 12 weeks postpartum)

• Each participant will have follow-up visits at home or healthcare facility whichever is preferred except the 6 weeks visit which as routine should be at the health care facility.

The following steps will be taken at the follow up visits:

- 1. Go to REDCap, using the participant's study ID-
 - Complete and submit the Edinburgh Postnatal Depression Scale (EPDS) e-form (Appendix xi) at 6 weeks visit.
 - Complete and submit the Maternal infant bonding scale e-form (Appendix xii) at 6 weeks visit.
 - Complete and submit the fatigue scale e-form (Appendix xiii) at 6-week visit.
 - Complete and submit the quality of life (WHOQOL BREF) scale e-forms (Appendix xiv) at 6 weeks visit.
 - Evaluate for the presence of any symptom and sign (adverse event(s) AEs)) and if any,
 complete and submit the adverse event e-form for all follow up visit.

The visit e-CRF will be available to you ONLY after completing and submitting the above steps on REDCap.

- Evaluate compliance to study drug and document in the e-CRF.
- Complete follow-up visits e-CRF (Appendix xv) and relevant source documents
- Re- supply study drug (control arm) in an amount sufficient to last until the next follow up visit up to the 6th week visit.
- Counsel and necessary referral (e.g., family planning clinic, psychosocial support etc.).

2. Additional steps

- Perform malaria rapid diagnostic test (RDT) with SD BIOLINE Malaria Ag P.f and complete the *Malaria POCT worksheet* as appropriate (2- and 6-week postpartum visits).
- Do hemoglobin concentration check with the haemoglobinometer at every follow up visit. And complete Hb check worksheet as appropriate.
- Take blood samples for laboratory tests as indicated for visit type and complete the blood sample collection log on REDCap. This sample can also be used for the hemoglobin concentration check.
- Counsel as appropriate based on any queries they might have about their health or that of their newborn/baby.

The research team at site will be responsible for the visits and attending to the participant and resupplying the participants with the study drugs at two weeks.

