Inclusion/exclusion criteria (S,D)		X				
Written informed consent (S)		X				
Socio-demographics/PMH (S,D)		X				
Concomitant medication (S,D)		Х	X	Х	Х	X
Clinical symptoms (S,D)		X	Х	Х	Х	X
Physical examination (S,D)		Х	Х	Х	Х	Х
Lab Tests (S,D)	Hb	Х	Х	Х	Х	X
	Malaria	Х	Х	Х		
	FBC	X	Х	Х		X
	Iron panel	Х		Х		X
	Maternal Serum P04 and other markers	Х	X (Ca, PO4 &	Х		
			ALP only)			
Intervention drug (FCM); S, D		X				
Control drug (FS); S, D		X	X	X		
Adverse Events (S, D)		Х	Х	Х	Х	Х
Edinburgh Postnatal Depression Scale (EPDS) (D)				Х		Х
Mother to infant bonding scale (D)				Х		X
Fatigue scale (D)				X		Х
Quality of life scale (D)				Х		X
Implementation data collection (D)						X
End of study (D)						X

Note: All Participants will be recruited from the postnatal wards from 6 hours after delivery, followed up at home or hospital two weeks later, seen again at six weeks, 12 weeks, and six months postpartum.

^{*} Iron panel comprises serum iron, serum ferritin, transferrin saturation and percentage transferrin saturation. FCM: Ferric carboxymaltose. FS: Ferrous sulphate. S: Source document. D: Database (REDCap e-forms).

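### Two secondary outcomes each name a time point with no scheduled data: iron indices at two weeks (3.1.2 e) and WHOQOL-BREF at enrollment (3.1.2 r)

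*Protocol*

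**What the plan says.** **Iron indices.** Outcome (e) in Protocol section 3.1.2 is "Change in mean serum ferritin, serum transferrin, serum iron and % transferrin saturation at two weeks and six weeks postpartum". Section 4.9 says the iron profile "will be done at baseline (enrollment), six weeks and six months postpartum". The iron panel row of Table 3 agrees: it is marked at baseline, six weeks and six months, and is blank at two and twelve weeks. For the phosphate and bone markers, by contrast, section 4.9 states a reduced two-week set: "2 weeks (Ca, PO4 and ALP only) and at 6 weeks postpartum". The follow-up procedures in 4.10.3 add no test of their own; blood is taken "as indicated for visit type and complete the blood sample collection log on REDCap".

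**Quality of life.** Outcome (r) is "Quality of life measured using the WHOQOL BREF at enrollment, six weeks, and six months post-partum". The enrollment steps in 4.10.2 cover randomization, the biodata and locator form, history, examination, the adverse event form, the enrollment e-CRF, blood samples and study drug. They do not mention WHOQOL-BREF. Section 4.10.3 calls for the form at the six-week visit and 4.10.5 at six months. Table 3 marks those two visits and leaves baseline blank.

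**The concern.** An outcome can be reported only at visits where its measurement is taken. The outcome list and the schedule disagree about two such visits, and sites work from the schedule. A statistical analysis plan cannot settle this, because it governs data that exist and cannot supply an unscheduled assay or questionnaire.

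For iron, the loss would be the early repletion contrast that (e) promises. Section 9.4 plans mixed models on repeated iron measures, and as scheduled these would have nothing between baseline and six weeks. For quality of life, the loss would be any change from baseline and any baseline adjustment. In both cases a listed time point without results could later look like selective reporting, although the cause is only a mismatch within the protocol.

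**Working it through.** No alpha, power or rate is involved, so the check sets the required time points against the scheduled ones.

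| Outcome | Required by 3.1.2 | Scheduled | Not covered |
|---|---|---|---|
| (e) four iron indices, as change | baseline (implied by change), 2 weeks, 6 weeks | baseline, 6 weeks, 6 months (4.9, Table 3) | 2 weeks |
| (r) WHOQOL-BREF | enrollment, 6 weeks, 6 months | 6 weeks (4.10.3), 6 months (4.10.5), same in Table 3 | enrollment |

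1. **Could this be a broken table?** No. The prose of 4.9 and of 4.10.2, 4.10.3 and 4.10.5 agrees with Table 3. Prose and table together contradict the outcome list.

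2. **Is another instruction hidden elsewhere?** For iron, 4.10.3 defers to the visit type. The tests scheduled at two weeks are hemoglobin, malaria, full blood count, calcium, phosphate and alkaline phosphatase. For quality of life, the content of the enrollment e-CRF (Appendix x) is not shown. However, WHOQOL-BREF is a separate form (Appendix xiv), and section 9.1 lists it among the other REDCap instruments, apart from the visit forms.

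3. **Is the mismatch general?** No. Two-week hemoglobin (outcome b) and two-week phosphate (outcome l) are scheduled. The depression, fatigue and bonding scales are both defined and scheduled at six weeks and six months.

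4. **Size.** Outcome (e) has 4 indices × 2 time points = 8 index-by-time results, of which 4 (those at two weeks) have no scheduled data. Outcome (r) has 3 time points, of which 1 has none. Outcomes (a) to (r) number 18, so 2 of 18 are affected. If every site follows Table 3, the gap applies to all 1,400 women.

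5. **What survives.** Baseline and six-week iron panels are both drawn, so the six-week change can be estimated. WHOQOL-BREF at six weeks and six months can be compared between arms, and randomization makes that comparison valid without a baseline score.

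**The case against.** The strongest reply is that little is lost. Only one time point of each outcome is affected, the primary outcome, sample size, interim rule and safety assessments are untouched, and outcome (r) does not define a change score. Nor does 9.4 specify a baseline-adjusted quality-of-life analysis. All of this stands, and it limits the severity.

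Four stronger readings are tempting, but the documents do not support them:

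- **That the two outcomes cannot be produced at all.** The remaining time points of both are scheduled and estimable.
- **That the data will never be collected and are certain to be missing for every woman.** The protocol shows only that collection is not scheduled. A site might act on 3.1.2 instead, and the enrollment e-CRF is not shown.
- **That the gap is wholly beyond repair.** This holds for baseline quality of life. For iron, serum is drawn at two weeks anyway, and section 14.3 provides for indefinite storage of a portion of the blood samples with consent. It does not say which visits' samples are kept, so a later assay is neither assured nor excluded.
- **That the six-month iron panel serves no purpose.** No iron outcome in 3.1.2 uses it, but 9.4 plans repeated-measures models of iron biomarkers. It also plans comparisons of anemia and iron deficiency in a sentence that names six weeks and six months.

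None of this removes the contradiction. Following the schedule as written leaves a stated time point of each outcome without data.

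**Conclusion.** The inconsistency is real and can be verified directly from the text. Two of 18 secondary outcomes each name one time point that the schedule does not cover: four iron indices at two weeks, and WHOQOL-BREF at enrollment. The conclusion assumes that sites follow 4.9, 4.10 and Table 3, and that the enrollment e-CRF does not itself contain the questionnaire. On those assumptions there will be no baseline quality of life, and two-week iron indices only if stored serum happens to be available and is assayed.

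This is an internal inconsistency, not a design choice. It should be fixed, because the correction is simple and a missed baseline score cannot be obtained later. It does not threaten the trial's main conclusion.

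**What to change.** Reconcile 3.1.2 (e) and (r) with 4.9, 4.10 and Table 3 in one amendment, made before any comparative data are seen.

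- **Iron.** Either add the panel to the serum already drawn at two weeks and mark it in 4.9 and Table 3, or remove two weeks from (e). Adding it costs the assays and possibly one more tube, but no extra visit. Removing it gives up the early contrast. In either case the six-month panel already drawn may be listed as a time point of (e).
- **Quality of life.** Either add WHOQOL-BREF at enrollment and mark it in Table 3, or delete enrollment from (r). If it is added, its place in 4.10.2 matters: randomization is step 1 there and the REDCap forms, including the enrollment e-CRF, are step 2. Simply attaching the questionnaire to that e-CRF would let women answer with their arm already known in an open-label trial. It should be completed after consent and before randomization. The form already exists in REDCap, so the added burden is the time to complete it.

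Rewording alone needs no new data collection, but it is not free of process: section 11.5 requires a written amendment with ethics committee approval.
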